7.2. Subject disposition

Subject disposition will be described.

A summary table with the description of the number of screened participants, the number of included participants, the number of randomised participants, the number of participants who completed the study and the number of participants who discontinued the study, classified by main reason of withdrawal, will be prepared by treatment group and overall for the subjects in the IS. Corresponding individual listings will be provided.

A summary table with the description of the number and percentage of subjects in each analysis set (IS, RS, SS, PDS and PKS) will be prepared by treatment group and overall. A specific listing of subjects excluded from analysis sets will be provided with the reason(s) for exclusion.

A summary table with the number and percentage of subjects at each visit will be prepared by treatment group and overall on the subjects in the RS. A specific listing with discontinued participants will be prepared. Listings with analysis sets, end of study status and visit dates will also be generated.

7.3. Protocol deviations

A summary table by treatment group and overall with the number and percentage of subjects presenting deviations relating to inclusion/exclusion criteria will be prepared for the subjects in the RS. A summary table by treatment group and overall with the number and percentage of subjects presenting other protocol deviations (all deviations judged relevant during the blind review meeting) will also be prepared by status of the deviations (minor/major). The corresponding listings will be provided with the status of the deviations.

8. Demographic data and baseline characteristics

The analyses of the demographic and baseline characteristics will be performed on the Randomised set.

8.1. Demographic data

The participants' demographic characteristics (age, sex, ethnicity, race, height, weight and BMI recorded at screening) will be summarised by treatment group and overall, and listed.

8.2. Other baseline characteristics

All parameters recorded before dosing (subjects' habits like tobacco, alcohol and caffeine consumption, diet) will be summarised by treatment group and overall, and listed.

Abnormal or positive results as well as all individual data for serology (presence of HIV antibodies, hepatitis B surface antigen (HBsAg), and hepatitis C virus (HCV) antibodies), urine drug screen (amphetamines, benzodiazepine, cocaine, opiates, barbiturate and cannabinoids) and alcohol breath test will be listed.

Birth control method will also be listed.

8.3. Medical and surgical history and procedures

Information on medical and surgical history (including blood donation) recorded at the screening visit and procedures will be coded according to the Medical Dictionary for Regulatory Activities (MedDRA) Version 22.0.

A table with the number and percentage of subjects having at least one previous/ongoing medical history or one surgical history will be generated by treatment group and overall. Previous/ongoing medical history will be listed as well as prior surgeries and concomitant surgeries.

8.4. Previous and concomitant medications

Information on previous and concomitant medications will be coded according to the WHO drug Dictionary version of March 2019.

A previous medication will be defined as a relevant treatment received by the participant within 2 weeks before the study product administration. A concomitant medication will be defined as a medication the participant takes during the study and until the last extra ambulatory V11 visit only if related to a reported AE, other than the study drugs, including any prescription or over-the counter drug (including vitamins, herbal and mineral supplements). If the date value does not allow allocation of a medication to the previous or concomitant category (missing or incomplete start or end date), this medication will be considered concomitant.

A table with the number and percentage of subjects having taken at least one previous medication and a table with the number and percentage of subjects having taken at least one concomitant medication will be generated by treatment group and overall (overall and by medication class [2nd level of Anatomical Therapeutic Chemical (ATC)] and medication drug name). Previous and concomitant medications will be listed separately.

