
Concomitant medications and lifestyle restrictions: Water intake is allowed during the infusion.
 
Any medication the participant takes during the study, and until the discharge visit, other than the study drugs, including any prescription or OTC drug (including vitamins, herbal and mineral supplements), is considered a concomitant medication. At the extra visits scheduled for ADA assessment (i.e. up to D180), only the medications that are administered in treatment of AEs will be considered concomitant medication.
 
Participants will be requested to comply with the following restrictions during the study and abstain from:
 
- Strenuous exercise, as judged by the Investigator, from the selection visit until after the discharge visit.- Use of prescriptions or OTC medications [including decongestants, antihistamines], and herbal medication (including herbal tea and St. John's Wort), within 14 days prior to study drug administration through the discharge visit, unless approved by the PI and Sponsor medical monitor. Occasional use of paracetamol at recommended doses is allowed. Specific rules apply for aspirin, corticosteroids and NSAIDS (see exclusion criteria 6, 7, 8 and 9).- Consumption of grapefruit, grapefruit juice, Seville oranges, Seville orange marmalade or other products containing grapefruit or Seville oranges from selection visit until after the discharge visit.- Consumption of any alcoholic beverages 24 hours before administration of study drug, during the in-patient period of the study and 24 hours prior to all other ambulatory visits, up until and including the discharge visit.- Smoking and using nicotine-containing products excluded for at least 3 months prior to the screening visit, and until after the discharge visit.- Use of Acetylsalicylic-Acid (ASA)-containing over-the-counter medications within 1 month prior to screening and until the discharge visit.- Consumption of any caffeine-containing products (e.g. coffee, tea, chocolate, or Coca-Cola like/ energy drinks): excluded from 24 hours prior to D1 until the end of the in-patient period. Limited to less than 500 mg/day of caffeine (as contained in 5 cups of tea or coffee or 8 cans of caffeine-containing soda or other caffeinated products per day) until the discharge visit.- Donation of blood (i.e. 500 mL) within 3 months before D1, throughout the study and for 3 months after the end of the study (D90 or D180). 
The compliance of the participant to these lifestyle restrictions will be checked at each visit.
 
Participants and their partners of childbearing potential must be willing to use 2 methods of contraception, one of which must be a barrier method, and participants will not donate sperm, from the selection visit and up to 90 days after the infusion.
 
Supplemental ADA samplings ("long-term follow-up of ADAs"):
 
At the additional samplings scheduled for ADA assessment after D180, only treatments given for Serious Adverse Drug Reactions (SADRs) will be considered concomitant medications, and they will be collected only in the Pharmacovigilance (PV) database.

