3.4. Visits

For cohorts from A to D, the study will include the following visits (see section 16.1.1):

	Cohorts A, B and C	Cohort D
Screening	from Day-28 to Day -2 (Visit V1)	
Randomisation	Day 1 (pre-dose, Visit V3)	
Treatment period	from Day -1 (Visit V2) to Day 5 (Visit V7)	from Day -1 (Visit V2) to Day 7 (Visit V8)
Discharge visit	Day 10 (\pm 2 days) (Visit V8)	Day 10 (\pm 2 days) (Visit V9)
Extra ambulatory visits for ADA analysis	Day 30 (\pm 3 days) (1 month, Visit V9) Day 90 (\pm 7 days) (3 months, Visit V10) Day 180 (\pm 7 days) (6 months, Visit V11)	Day 30 (\pm 3 days) (1 month, Visit V10) Day 90 (\pm 7 days) (3 months, Visit V11) Day 180 (\pm 7 days) (6 months, Visit V12)

All participants will receive a single intravenous dose of Ir-CPI/Placebo at Day 1, given as a 6-hour infusion.

4. Sample Size

The number of participants is not based on statistical power considerations. A sample size of 8 participants per panel (i.e., 6 active and 2 placebo) was chosen based on the design of similar SAD studies and is considered adequate to provide an initial assessment of the safety and tolerability profile of Ir-CPI.

5. Changes to the planned analysis from protocol

The following changes are added compared to the planned analysis detailed in the study protocol:

- Addition of the Screened set (defined as all of the subjects having signed an informed consent form) (see section 7.1).
- Orthostatic hypotension and abnormal HR will not be derived because there are not standing vital signs measured during the study.
- Only the Part 1 was performed with 4 cohorts (A, B, C and D) (instead of Part 1 with 5 cohorts and Part 2 with 3 cohorts) and with the following dose modifications discussed during SRC meetings (see minutes of these meetings):
 - Cohort A: Ir-CPI 1.5 mg/kg;
 - Cohort B: Ir-CPI 3 mg/kg;
 - Cohort C: Ir-CPI 6 mg/kg;
 - Cohort D: Ir-CPI 9 mg/kg.
- In exploratory objectives, the investigation of the ADA capability to neutralize drug activity was not performed, and the assessment of the PK of Ir-CPI in urine was also not done.
- Addition of statistical analysis of AUC_{0-96h} and AUC_{0-last} (see section 9.2.2).

6. Statistical considerations

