16. All participants will receive a single intravenous dose of Ir-CPI/Placebo given as a 6-hour infusion. Post dose is measured after the beginning of infusion. A light breakfast (2 slices of bread with ham or cheese and jam, glass of water) can be given between 2h and 1h before start of infusion. Lunch will be served after completion of the infusion.
17. Cluster A (central lab): the effect of Ir-CPI on PD aPTT (central lab) (not to be confused with safety aPTT) and on FXI/FXII activities will be measured on D1: pre-dose, then at 30min, 60min, 90min, 2h, 4h, 6h, 6h30, 7h, 7h30, 8h, 10h, 12h, 16h post-dose, then on D2 (24h), D3 (48h), D4 (72h), D5 (96h) and discharge visit. In case of infusion less than 6 hours and besides assessment at predose, 30 min, 60 min, 90 min, 2h and 4h after start of infusion, Cluster A (central lab) parameters should be measured at the end of infusion, then 30 min, 60 min, 90 min, 2h, 4h, 6h, 10h, then 18h, 42h, 66h and 90h after the end of infusion and then at the discharge visit.
18. Cluster B (local lab) the effect of Ir-CPI on PT (sec and INR), D-dimers, fibrinogen, hsCRP and TNF α will be measured on D1, predose then at 2h, 4h, 6h, 8h, 12h post-dose, on D2 (24h post-dose), D3 (48h) and D4 (72h) and discharge visit. In case of infusion less than 6 hours and besides assessment on D1 at predose and at 2h and 4h after start of infusion, Cluster B (local lab) parameters will be measured at the end of infusion, then 2h, 6h, 18h, 42h and 66h after the end of infusion and then at the discharge visit.
19. CysC (central lab) will be collected at screening, then from D1 to D4: Predose (D1), 24h (D2), 72h postdose (D4), and then at the discharge visit.
20. Blood samples for Ir-CPI PK will be done on D1, pre-dose and at 30min, 60min, 90min, 2h, 4h, 6h, 6h30, 7h, 7h30, 8h, 10h, 12h, 16h, then D2 (24h), D3 (48h), D4 (72h) and D5 (96h) post-dose (after start of infusion). In case of infusion less than 6 hours, blood sample for Ir-CPI pharmacokinetics will be done at the end of infusion then 30min, 60min, 90min, 2h, 4h, 6h, 10h, 18h, 42h, 66h and 90h after end of infusion.
21. ADA analysis sample: pre-dose on the day of infusion, at the discharge visit, on D30 and on D90.
22. D180 only if ADAs are detected in the D90 samples.
23. Urine collections for PK assay are to be done at these intervals predose, [0-6h], [6-12h] and [12-24h] after start of infusion. Urinary NGAL, microalbuminuria and KIM-1 will be assessed.

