16.1.2. Part 1: Single 6-hour infusion for Cohort D

Assessments	Screening visit [1]	Treatment Period							Discharge Visit	Extra ambulatory visits for ADA analysis
	Visit 1 (V1) D-28 to D-2	V2 D-1	V3 D1 [2]	V4 D2 [6]	V5 D3 [6]	V6 D4	V7 D5	V8 D7	V9 D10 ± 2d	V10: D30 (±3d), V11: D90 (±7d) V12: D180 (±7d) [23]
Screening / Administrative / Other Assessments										
Informed consent	X									
Demography [3]	X									
Inclusion / exclusion criteria	X	X								
Medical and medication history	X									
Life restriction monitoring		X			X	X	X	X	X	
Drug / alcohol screen[4]	X	X								
Serology[5]	X									
Randomisation to treatment			X							
In-patient period [6]		←-----→								
Safety Assessments										
Physical exam[7]	X	X		X[7]	X[7]				X	
Brief physical exam[8]			X							
Vital signs[9]	X		X	X	X	X			X	
Telemetry (including SpO ₂)[10]		↔								
Height and BMI	X									
Weight	X								X	
Faeces collection (Hemoccult® test)	X	←-----→								
Supine 12-lead ECG[11]	X		X	X	X	X			X	
Serum chemistry[12]	X		X	X		X			X	
Haematology [12]	X		X	X		X			X	
Exposure to tick bites [13]			X						X	X
Anti-Borrelia immunity (IgG/IgM) [14]			X							
Safety aPTT[15]	X		X	X	X	X	X	X	X	
Urinalysis[16]	X		X	X		X			X	
Adverse event monitoring	←-----→									
Concomitant medication monitoring	←-----→									Only if related to the reported AE

Assessments	Screening visit [1]	Treatment Period							Discharge Visit	Extra ambulatory visits for ADA analysis
	Visit 1 (V1) D-28 to D-2	V2 D-1	V3 D1 [2]	V4 D2 [6]	V5 D3 [6]	V6 D4	V7 D5	V8 D7	V9 D10 ± 2d	V10: D30 (±3d), V11: D90 (±7d) V12: D180 (±7d) [23]
Study Drug Administration / Pharmacokinetic / Pharmacodynamic Assessments										
Study drug administration [17]			X							
PD samples cluster A: PD aPTT (central lab) and FXI/FXII activities [18]			X	X	X	X	X	X	X	
PD samples cluster B [19]			X	X	X	X			X	
CysC samples [20]	X		X	X	X	X			X	
Blood PK samples [21]			X	X	X	X	X	X		
Immunogenicity Testing (ADA) [22]			X						X	X [23]
Urine collection [24]			←→							

NOTE: postdose is defined as « after start of infusion »

1. Screening procedures must occur within 28 days up to 2 days before study drug administration.
2. The results of the analysis of the D1 predose samples are collected to establish baseline references and are not needed before administration.
3. Demography includes: year of birth, age, sex, ethnicity and race.

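### SAP 8.4 closes the concomitant-medication window at a visit number (V11) that is not the last extra visit for cohort D participants seen at D180

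*SAP*

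**What the plan says.** SAP 8.4 (Previous and concomitant medications) defines a concomitant medication as one taken during the study and "until the last extra ambulatory V11 visit only if related to a reported AE". It makes no distinction between cohorts. The definition feeds a table of the number and percentage of subjects with at least one concomitant medication, by treatment group and overall.

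SAP 3.4 (Visits) numbers the extra visits differently by cohort, because cohort D has an added D7 visit. For cohorts A, B and C it gives "Day 180 (\pm 7 days) (6 months, Visit V11"). For cohort D it gives "Day 90 (\pm 7 days) (3 months, Visit V11") and then "Day 180 (\pm 7 days) (6 months, Visit V12"). The flow charts in SAP 16.1.1 and 16.1.2 agree with this numbering.

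The protocol (Synopsis, repeated in Section 6.3) sets the period without visit numbers: "At the extra visits scheduled for ADA assessment (i.e. up to D180), only the medications that are administered in treatment of AEs" count as concomitant medication. The cohort D flow chart in SAP 16.1.2 has one column for V10 to V12, and its concomitant-medication row reads "Only if related to the reported AE". The D180 visit is conditional in every cohort: "D180 only if ADAs are detected in the D90 samples".

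**The concern.** The sentence in SAP 8.4 is the inclusion rule for a table by dose group, and monitoring of concomitant medication is a listed component of the primary safety endpoint (Protocol Section 4). Cohort D is the 9 mg/kg group, the highest dose given. If a programmer follows the visit number, AE-related medication taken between D90 and D180 would count at the three lower doses and not at the top dose. The same would apply to any cohort D placebo participant with a D180 visit, inside the pooled placebo column.

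The AE tables have no matching cut. SAP 13.1 records AEs to the end of the study, which Protocol Section 5.4 places at D90, or at D180 where ADAs are detected. A late AE in cohort D could then be tabulated while its treatment was missing from the medication table.

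**Working it through.** There is no stated figure to reproduce. The check maps visit labels to study days, using SAP 3.4 and the two flow charts.

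| Participant | Last extra visit held | Day of V11 | Do the last visit and V11 agree? |
|---|---|---|---|
| Cohorts A–C, no ADAs at D90 | V10 (D90) | not held | No, but no later visit is planned, so no effect |
| Cohorts A–C, ADAs at D90 | V11 (D180) | D180 | Yes |
| Cohort D, no ADAs at D90 | V11 (D90) | D90 | Yes |
| Cohort D, ADAs at D90 | V12 (D180) | D90 | No: the two readings give different cut-offs |

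Only the last row matters. For those participants:

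- Nominal gap between the readings: 180 − 90 = 90 days, which is 90/180 = 50% of the period from dosing.
- With the ±7-day windows, V11 falls on D173 to D187 in cohorts A–C and on D83 to D97 in cohort D. The gap between cohorts is then 173 − 97 = 76 to 187 − 83 = 104 days.

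These day counts are nominal. The Part 1 schedule of activities in the protocol (footnote 24 for cohorts A–C, footnote 25 for cohorts D and E) says that the D180 visit took place on one common day for all participants, whatever their dosing date. Protocol Section 7.4 requires at least 7 days between the first participants of consecutive panels. The first participants of A and D were therefore dosed at least 3 × 7 = 21 days apart. A single calendar date then falls on study days at least 21 apart for those two, if both attended. The ±7-day window is only 14 days wide. The real gap may therefore differ from 90 days, and a fixed study-day limit would not match the visits held.

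Nothing indicates a deliberate change. SAP Section 5, which lists departures from the protocol analysis, does not mention this window, and neither SAP appendix revises it.

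**The case against.** The best reply is that the sentence does not clearly order a D90 cut. It also says during the study and refers to the last extra ambulatory visit, which in cohort D is V12 when D180 is held. The protocol, the cohort D flow chart and the AE period all point to D180. SAP 8.4 has only two categories, previous and concomitant, so it has no place for a collected record that falls after the window. The likely explanation is a visit number carried over from cohorts A to C. This stands: the rule contradicts itself, and a programmer could follow either part of it.

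Three stronger readings are tempting, and the documents do not support them.

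- *The top dose is counted over a shorter period, so its result is biased downward.* That follows only from the visit-number reading, and only for participants with a D180 visit. Those without ADAs at D90 finish at D90 in every cohort.
- *The pooled placebo column mixes six participants followed to D180 with two followed to D90.* This needs all six placebo participants in A to C to have had ADAs at D90. They received saline, and Protocol Section 3.2 reports ADAs in 2 of 50 healthy Belgian volunteers. A split of that kind is not expected.
- *The 9 mg/kg percentage is understated by 16.7 points.* This is 1/6, the effect of one omitted participant among the six active. In the row for any medication, that participant would need ADAs at D90, a treated AE after D90 and no other concomitant medication in the study. It is not an expected effect.

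The AE itself would still be tabulated, and additional therapy is recorded with each AE (Protocol Section 9.6.1). The treatment would not be lost from the data.

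**Conclusion.** Wrong as written, minor severity. The label mismatch is certain. For any cohort D participant with a D180 visit, SAP 8.4 contradicts itself, the cohort D flow chart and the protocol. Whether the table would be affected depends on which part of the sentence is programmed.

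On the visit-number reading, the affected period is nominally 90 days, and any error can only lower the count at 9 mg/kg or among cohort D placebo participants. The documents do not give the number of cohort D participants with a D180 visit or the number of AE-related medications after D90. After discharge only AE-related medication counts, and the table is descriptive with no test. The effect is therefore probably small or nil. The case for correcting the sentence is that a table rule should not depend on which of two conflicting terms is followed.

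**What to change.** In SAP 8.4, replace the reference to V11 with: *the participant's last extra ambulatory visit (D90, or D180 where performed: V11 for cohorts A–C, V12 for cohort D)*. Program the cut-off from the actual date of that visit for each participant. A fixed day-180 limit should be avoided because the D180 visit was held on one calendar day for all participants, and such a limit could drop records collected at the real last visit in the earlier cohorts.

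The cost is one sentence and one derivation, with no new data. If the table already exists, it is enough to check whether any cohort D medication starting after the V11 date was left out, and to record the answer. The change brings the table into line with the protocol, the flow charts and the AE tables.

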8.5. Compliance

A listing with IMP administration dates and times will be generated. Time of meals intake will also be listed.

9. Pharmacokinetic data

The pharmacokinetic analysis will be performed on the PKS.

9.1. Generalities

The following rules for **PK parameter calculation** will be used:

- Actual sampling times will be used for deriving PK parameters.
- If an entire concentration-time profile is below the limit of quantification (BLQ), BLQ values will not be replaced and the profile will be excluded from the PK analysis.
- For plasma concentrations, all BLQ values occurring prior to the first detectable concentration and negative values will be replaced by "0".
- Embedded BLQ values (BLQ values between two measurable concentrations) will be treated as missing.
- All BLQ values occurring after the first detectable plasma concentration at the end of infusion: if there are several consecutive ones, the first one will be replaced by the lower limit of quantification (LLOQ) divided by 2 ("LLOQ/2") and the following ones by missing.
- If the pre-dose concentration is $\leq 5\%$ of the C_{max} value for a particular subject, that subject's data, without any adjustments, may be included in all pharmacokinetic and

statistical analysis. If the pre-dose value is $> 5\%$ of C_{max} , two analyses will be performed: one with the pre-dose value and the other one with the pre-dose value replaced by 0.

- If there are late positive concentration values following 2 BLQ concentration values in the terminal phase, these values will be evaluated. If these values are considered to be anomalous, they will be set to missing.
- Some conditions for PK parameters have to be fulfilled:
 - 1) the percentage of the extrapolated AUC should not exceed 20 % of the AUC_{0-inf} of each individual profile,
 - 2) the elimination rate constant should be determined over a time interval equal to at least $2 \times t_{1/2}$,
 - 3) the determination of λ_z should use only those data points judged to describe the terminal log-linear decline resulting in an adjusted coefficient of determination value $R^2 > 0.7$, and a minimum of 3 data points will be used in calculating λ_z excluding C_{max} .

If these conditions are not fulfilled, the following unreliable PK parameters will not be calculated, will be considered not determined (ND) in the listings and will be excluded from the analysis:

- 1) if extrapolated AUC $> 20\%$: AUC_{ext} , AUC_{0-inf} , CL and Vd_z ;
- 2) if the time interval used for the determination of the elimination rate constant is inferior to $2 \times t_{1/2}$ or if the adjusted $R^2 < 0.7$: λ_z , $t_{1/2}$, AUC_{0-inf} , R^2 , CL and Vd_z .

The following rules for **plasma concentration versus time graphic representation** will be used:

- No graphic representation will be done if all values are BLQ.
- BLQ values occurring prior to the first detectable concentration will be replaced by "0".
- Embedded BLQ values (BLQ values between two measurable concentrations) will be treated as missing.
- All BLQ values occurring after the first detectable plasma concentration at the end of infusion: if there are several consecutive ones, the first one will be replaced by the lower limit of quantification (LLOQ) divided by 2 ("LLOQ/2") and the following ones by missing.

The following rules for **mean plasma concentration calculation** will be used:

For BLQ concentrations before the first detectable concentration:

- If more than (or equal to) half of the values are either BLQ values replaceable by zero and/or numeric values: statistics will be calculated with the replaceable and numeric values.
- If more than half of the values are BLQ values not replaceable by zero (i.e., subjects for whom all values are BLQ): only the maximum will be presented and the other statistics will be considered BLQ.

For BLQ concentrations after the first detectable concentration:

- If more than (or equal to) half of the values are not BLQ: statistics will be calculated with missing and replaced BLQ values.

- If more than half of the values are BLQ: only the maximum will be presented and the other statistics will be considered BLQ.

For summary statistics for PK parameters:

- If more than (or equal to) half of the values are **not ND and not missing**: statistics will be calculated with the available values.
- If more than half of the values are **ND or missing**: only the minimum, median and maximum of the available numeric values will be presented. All other statistics will not be calculated and will be presented as ND.

All BLQ concentrations and missing data will be labelled as such in the concentration data listings.

